7.1.4 Pre-Existing Conditions

In this trial, a pre-existing condition (i.e., a disorder present before the adverse event reporting period started) should not be reported as an adverse event unless the condition worsens during the adverse event reporting period.

7.1.5 Procedures

Diagnostic and therapeutic non-invasive and invasive procedures, such as surgery, should not be reported as adverse events. However, the medical condition for which the procedure was performed should be reported if it meets the definition of an adverse event. For example, an acute appendicitis that begins during the adverse event reporting period should be reported as the adverse event and the resulting appendectomy noted under Comments.

7.1.6 Laboratory Test Abnormalities

Laboratory test value abnormalities will be reported as an AE if they satisfy one or more of the following conditions for clinical significance:

1. Accompanied by clinical symptoms
2. Leading to a change in study medication (e.g. Dose modification, interruption or permanent discontinuation)
3. Requiring a change in concomitant therapy (e.g. Addition of, interruption of, discontinuation of, or any other change in a concomitant medication, therapy or treatment).

Please note: any laboratory result abnormality fulfilling the criteria for a serious adverse event (SAE) should be reported as such, in addition to being recorded as an adverse event in the CRF.

7.2 GRADING OF ADVERSE EVENTS

All adverse events will be graded by the Investigator using the scale below.

1=Mild	Discomfort noticed but no disruption of normal daily activity
2=Moderate	Discomfort sufficient to reduce or affect daily activity
3=Severe	Inability to work or perform normal daily activity

7.3 CAUSALITY

Relationship of all adverse events and serious adverse events to the study interventions (causality) should be assessed by the investigator as follows:

- **Unrelated:** There is not a reasonable possibility that the adverse event may have been caused by the study drug.

- **Possibly related:** The adverse event may have been caused by the study drug, however there is insufficient information to determine the likelihood of this possibility.
- **Related:** There is a reasonable possibility that the adverse event may have been caused by the study drug.

7.4 EXPECTEDNESS

Adverse events and serious adverse events will also be assessed according to the following categories:

- **Expected (anticipated):** the event is identified in nature, severity, or frequency in the investigator brochure, product monograph or in the protocol .
- **Unexpected (unanticipated):** the event is not identified in nature, severity, or frequency in the investigator brochure, the product monograph or in the protocol.

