1.3 DIRECT FACTOR XA INHIBITORS IN PAD

Direct FXa inhibitors, such as rivaroxaban, are oral agents that inhibit factor Xa leading to a decrease in thrombin formation and potentially, a decrease in platelet activation. Rivaroxaban is detected 2–4 hours after oral administration, has half-life of 7 to 11 hours, and is associated with few drug interactions³⁴. In phase III randomized trials; rivaroxaban and apixaban have shown to be effective for stroke prevention in patients with AFIB^{35,36}; DVT prevention after surgery³⁷⁻³⁹; and treatment of VTE⁴⁰⁻⁴². In patients with ACS⁴³, rivaroxaban reduced mortality, ACS, stroke, and stent thrombosis, although, along with these benefits is an increased risk of major bleeding⁴³. It is widely believed that activated FXa has limited functions other than serving as the principal mediator of thrombin generation from prothrombin via the prothrombinase complex⁴⁴. Factor Xa occupies a critical juncture in the coagulation cascade⁴⁵ and controls thrombin generation. The activation of one molecule of FXa results in the generation of 1000 molecules of FIIa⁴⁶. FXa initiates intracellular signaling in various cell types of the cardiovascular system, preferentially mediated via PAR-2⁴⁷ which contributes to the production of proinflammatory cytokines, tissue factor up-regulation, SMC proliferation, and the release of vascular endothelial growth factor. Inhibition of FXa prevents thrombin generation via inhibition of free, prothrombinase-bound, and clot-associated Factor Xa and consequently attenuates thrombus-associated procoagulant activity³⁴. This explains why compared to heparin, that allows persistent thrombin generation and direct thrombin inhibitors that aggravate thrombin generation, direct FXa inhibitors allow for small amounts of thrombin generation and protein C activation. The potential effects of FXa inhibition for the prevention of restenosis following PTA could be caused by the reduction of clot-induced mitogenesis and inflammatory gene expression in human vascular SMC⁴⁸; inhibition of the procoagulant activity of activated monocytes and macrophages⁴⁹; and effects on the intrinsic coagulation pathways. To our knowledge only one study conducted in healthy volunteers suggested that rivaroxaban reduced thrombus associated mitosis of SMC of the aortic arch⁴⁸. In animal models, vascular remodeling and myointimal formation were reduced on targeted delivery of nonspecific factor Xa inhibitors^{34;44;50-52}. Animal models have suggested that rivaroxaban decreases mRNA expression of inflammatory mediators, such of IL-6, TNF- α , MCP-1, and Egr-1 promoting arterial plaque stability. In stent thrombosis models, rivaroxaban either alone or in combination with ASA+/-clopidogrel initiated a dose-dependent inhibition of FXa-induced, tissue factor-induced, thrombin-induced platelet aggregation, and ADP-induced platelet aggregation⁵³. In conclusion, evidence suggests that

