1.4 RATIONALE FOR TREATMENT SCHEDULES

We selected rivaroxaban 2.5mg twice daily because:

1. Rivaroxaban is the only FXa inhibitor that has shown to improve cardio-vascular outcomes in patients with¹ and without ACS^{2, 3}; furthermore, it has shown to reduce systemic non-CNS systemic⁴ embolism and stent thrombosis post PTA⁵.
2. A 2.5 mg twice daily dose appears to provide the best risk/ratio in combination with antiplatelet agents for the prevention of vascular events in patients treated with antiplatelet agents. The risk of bleeding in patients receiving rivaroxaban and antiplatelet appears to be increased regardless of the treatment indication. Mega et al suggested that a 10 mg daily dose of Rivaroxaban in combination with aspirin was associated with a 2.2% risk of TIMI major bleeding whereas it was 0% in those treated with a 5 mg daily dose plus aspirin. In participants treated with a total daily dose 5 mg of rivaroxaban, those who received 2.5 mg twice daily had a lower bleeding risk than those treated with 5 mg once daily (1.4 vs. 2.9%); furthermore twice daily dosing was associated with a lower number of cardiovascular events (6.6 vs. 9.4%)(6). In ATLAS ACS 2–TIMI 51, the 2.5-mg twice-daily dose of rivaroxaban compared with placebo was associated with reductions of 34% for cardiovascular death and 32% for all-cause death, which were not seen with the 5-mg twice-daily dose(1).
3. Although previous studies looking at the role of anticoagulation post PTA for CLI have used prophylactic doses of LMWH(7), our concern is that patients with CLI are older and sicker and a dose of rivaroxaban of 10 mg once daily in combination with aspirin will be associated with a higher bleeding risk without significant improvement in outcomes.

We selected ASA-clopidogrel as comparator because it is the treatment recommended by guidelines^{7,8}, and is used by 50% of vascular surgeons in Canada

Since optimal medical management to decrease restenosis and thrombosis rates following PTA would make an important contribution to the sustained success of endovascular treatment, the proposed study will evaluate indicators of the effect of rivaroxaban in patients with CLI requiring PTA.

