7.5.3 Serious Adverse Events Reporting

SAEs require prompt or immediate reporting to the QI or delegate. The QI is ultimately responsible for reporting the SAEs to Health Canada, the OHSNREB, the Data and Safety Monitoring Board and Bayer.

Reporting to Health Canada

Serious adverse events that are both unexpected and related or possibly related are subject to expedited reporting to Health Canada. SAEs that are expected or that are unrelated to the study drug are not reportable.

Report must be filed in the cases:

- I. where the SAE is neither fatal nor life-threatening; within 15 days after becoming aware of the information
- II. where it is fatal or life-threatening, immediately where possible and, in any event, within 7 days after becoming aware of the information

Within 8 days after having informed Health Canada of the SAE, the Qualified investigator will submit as complete as possible, a report which includes an assessment of the importance and implication of any findings.

Each SAE which is subject to expedited reporting should be reported individually using the RIFLE SAE form (see Appendix 2).

Any updated follow up information that becomes available regarding the SAE should be reported in a follow up report.

Reporting to the OHSNREB

All SAEs, will be reported to the OHSNREB as per their guidelines.

Reporting to the Data Safety Monitoring Board (DSMB)

SAEs, that are related or possibly related and unexpected will be reported immediately to the Chair of the DSMB .

All SAEs, whether related to the study interventions or not will be summarized in a table, and provided to the DSMB before each scheduled DSMB meeting

Reporting to Bayer

SAEs will be reported to Bayer as per procedure outlined in the grant agreement.

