8.1.2.2 BLEEDING

Bleeding will be classified as per the Thrombolysis in Myocardial Infarction (TIMI) bleeding classification scheme:

Major Bleeding:

- Any intracranial bleeding
- Clinically significant overt signs of bleeding associated with a drop in hemoglobin of > 50 g/L (or, when hemoglobin is not available, an absolute drop in hematocrit of > 15%),
- Fatal bleeding that directly results in death within 7 days.

Minor Bleeding:

- Any clinically overt sign of bleeding (including imaging) that is associated with a fall in hemoglobin of 30 to 50 g/L (or, when hemoglobin is not available, a fall in hematocrit of 9 to 15%).
- Any overt sign of hemorrhage that meets one of the following criteria and does not meet criteria for a major or minor bleeding event, as defined above
 - Requiring intervention (medical practitioner-guided medical or surgical treatment to stop or treat bleeding, including temporarily or permanently discontinuing or changing the dose of a medication or study drug)
 - Leading to or prolonging hospitalization
 - Prompting evaluation (leading to an unscheduled visit to a healthcare professional and diagnostic testing, either laboratory or imaging)

Minimal Bleeding:

- Any overt bleeding event that does not meet the criteria for major or minor bleeding listed above
- Any clinically overt sign of bleeding (including imaging) that is associated with a fall in hemoglobin < 30 g/L (or, when hemoglobin is not available, a fall in hematocrit of < 9%).

Bleeding will be further identified using the following criteria:

- Significant: major bleeding or minor bleeding requiring medical attention.
- Instrumented: any bleeding that occurs as a result of an invasive procedure.
- Spontaneous: any bleeding that is not the direct result of an invasive procedure (e.g. gingival bleeding, epistaxis, gastrointestinal bleeding).

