APPENDIX 4: PRODUCT INFORMATION

Rivaroxaban 2.5 mg

Source:	Bayer Canada
Brand Name	XARELTO
Manufacturer	Bayer
Dosage form	Film-coated, round, biconvex, light red immediate release tablets of 6 mm diameter for oral use.
Daily dose:	2 tablets (2.50 mg twice daily every 12 hours)

Rivaroxaban will be supplied free of charge to all study participants randomized in treatment arm 1. Rivaroxaban tablets will be stored at the Ottawa Hospital Research Pharmacy. Each bottle will be labeled according to Food and Drug Regulations Division 5 Part C requirements as Rivaroxaban 2.5 mg is not a product currently approved in Canada.

Acetylsalicylic acid (ASA) 81 mg

Source:	Commercial
Brand Name	As per hospital formulary
Manufacturer	As per Hospital formulary
Dosage Form	Tablets
Daily dose:	1 tablet (ASA 81 mg) OD

ASA will be supplied free of charge to all study participants. Bottles will be labeled according to Food and Drug Regulations Division 5 Part C requirements as although ASA is standard of care for the proposed indication, it is an off label use according to the Product Monograph .

Clopidogrel 75 mg

Source:	Commercial
Brand Name	As per Hospital Formulary
Manufacturer	As per Hospital Formulary
Dosage Form	Tablets
Daily dose:	1 tablet (Clopidogrel 75 mg)OD

Clopidogrel will be supplied free of charge to all study participants randomized in treatment arm 2. Proposed indication, dose and route are within the parameters of the NOC : Clopidogrel is approved in Canada for the secondary prevention of atherothrombotic events (myocardial infarction, stroke and vascular death) in patients with atherosclerosis documented by stroke, myocardial infarction, or established peripheral arterial disease (Plavix Product monograph) . The recommended dose of is 75 mg once daily with or without food.

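### Section 7.4 allows a drug-related SAE to be classed as expected on one matching attribute, so one more severe or more frequent than listed can miss expedited reporting

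*Combined protocol and SAP*

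**What the plan says.** Section 7.4 of the combined protocol and SAP sorts adverse events into two classes. An event is expected when "the event is identified in nature, severity, or frequency in the investigator brochure, product monograph or in the protocol". It is unexpected when "the event is not identified in nature, severity, or frequency in the investigator brochure, the product monograph or in the protocol". Both definitions join the three attributes with *or*, and both place the protocol beside the brochure and the monograph as a reference source.

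Section 7.5.3 ties the regulatory route to that label. It says "Serious adverse events that are both unexpected and related or possibly related are subject to expedited reporting to Health Canada", and then "SAEs that are expected or that are unrelated to the study drug are not reportable". The 15-day and 7-day deadlines come after that restriction. No separate route is given for a fatal or life-threatening event labelled expected.

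Other oversight depends less on the label:
- **Ethics board:** section 7.5.3 sends it all SAEs.
- **DSMB:** section 7.5.3 tabulates all SAEs before each scheduled meeting, but limits immediate notice to the Chair to related or possibly related SAEs that are also unexpected. Section 9.5.1 has the DSMB told at once of any SAE potentially related to study drug, with no condition on expectedness.
- **SAE form (Appendix 2, item 23):** it adds a third box, *More prevalent*, which section 7.4 does not define and section 7.5.3 does not mention.

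On bleeding, section 1.3 says of rivaroxaban in acute coronary syndrome that "along with these benefits is an increased risk of major bleeding". Section 1.4 says "The risk of bleeding in patients receiving rivaroxaban and antiplatelet appears to be increased regardless of the treatment indication".

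**The concern.** An expectedness rule should separate events that behave as already described from events that do not, including a known reaction in a worse form or at a higher rate. With *or* in the definition of expected, a match on nature alone is enough, so greater severity or frequency does not remove the label. Admitting the protocol as a source widens this further. It is not written as a list of expected reactions, yet it discusses bleeding on rivaroxaban in general terms.

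At stake is whether the regulator hears promptly of a related SAE that is worse than the safety documents describe. That matters here because Appendix 4 states that "Rivaroxaban 2.5 mg is not a product currently approved in Canada", section 7.6 sets no formal stopping rules, and section 9.5.1 describes one scheduled DSMB meeting, midway through the trial.

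**Working it through.** There is no figure in the plan to reproduce. The check sets sections 7.4 and 7.5.3 side by side and counts cases.

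**Step 1: the patterns.** Each of nature (N), severity (S) and frequency (F) is either identified in a reference source or not, which gives 2 × 2 × 2 = 8 patterns. Expected is read literally, as at least one attribute identified. Unexpected can be read in two ways: none identified (reading A), or at least one not identified (reading B).

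| N | S | F | Expected (any one) | Unexpected, A (none) | Unexpected, B (any one missing) |
|---|---|---|---|---|---|
| yes | yes | yes | yes | no | no |
| yes | yes | no | yes | no | yes |
| yes | no | yes | yes | no | yes |
| yes | no | no | yes | no | yes |
| no | yes | yes | yes | no | yes |
| no | yes | no | yes | no | yes |
| no | no | yes | yes | no | yes |
| no | no | no | no | yes | yes |

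**Step 2: the counts.**
- Expected, literal reading: 8 − 1 = 7 of 8.
- Expected, if all three attributes had to match: 1 of 8.
- Patterns on which those two rules differ: 7 − 1 = 6.
- Patterns that are both expected and unexpected under reading B: the same 6.
- Of those 6, nature is identified in 3. These are the practical cases: a known kind of event that is more severe, more frequent, or both.

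The patterns are not equally likely, so these counts describe the rule and are not probabilities.

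**Step 3: a related bleed whose nature is named but whose severity is not.** Sections 1.3 and 1.4 identify bleeding, and major bleeding, as a rivaroxaban risk, so nature is identified in the protocol.
- Reading A: the event is expected only. Section 7.5.3 makes it not reportable to Health Canada and gives the DSMB Chair no immediate notice.
- Reading B: the event meets both definitions. Section 7.5.3 then makes it subject to expedited reporting by one sentence and not reportable by the next.

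**Step 4: whether other text settles it.** It does not. The 7-day deadline applies only to an SAE already classed as unexpected and related or possibly related. The *More prevalent* box lets an investigator record higher frequency, but no reporting rule is attached to it. The severity scale in section 7.2 stops at severe and has no life-threatening or fatal grade. Section 9.5.1 restores immediate DSMB notice but conflicts with section 7.5.3, and it does not touch the Health Canada route.

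**The case against.** A reader might infer that a fatal or intracranial bleed on rivaroxaban *is* expected under this protocol and necessarily escapes expedited reporting. The documents do not support that, for three reasons.

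- Reading B of unexpected is open, and under it the same bleed also qualifies for expedited reporting. The text permits the expected label without compelling it.
- The phrase "Fatal bleeding that directly results in death within 7 days" and the mention of intracranial bleeding come from the outcome definitions in section 8.1.2.2. Nothing says that a defined outcome counts as an expected reaction. For cardiovascular events the case is weaker still, since the hypothesis in section 2 is that rivaroxaban reduces them.
- The investigator brochure and product monograph are not among the documents. If they list such bleeds at that severity, some would remain expected under a corrected rule.

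A reader might also infer that one misclassified event removes the safety signal. It does not. All SAEs reach the ethics board and the DSMB tables, SAEs go to the rivaroxaban supplier under the grant agreement, and section 9.5.4 has bleeding and cardiovascular events adjudicated blind.

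Nor should the 1.4% in section 1.4 be used to put a probability on the harm. It is an unspecified bleeding risk from a cited trial, and the same paragraph quotes 0% TIMI major bleeding for a 5 mg daily dose plus aspirin.

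Finally, frequency is hard to judge on one case. One event in 40 participants is 1/40 = 2.5%. If the arms are equal, which the protocol does not state, it is 1/20 = 5% of an arm, above that 1.4%. Read naively, a first listed bleed would always look too frequent. That point stands, and the repair has to deal with it.

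What remains is that both readings fail. One lets a worse-than-listed event go unexpedited; the other makes the two classes overlap.

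**Conclusion.** The concern holds as a defect in a stated rule. Sections 7.4 and 7.5.3 together allow a related SAE that is more severe or more frequent than listed to be classed as expected and not sent to Health Canada. On the alternative reading they give contradictory instructions for it. Six of the eight attribute patterns are affected, three of them with the nature identified. The consequence is confined to the Health Canada route and to section 7.5.3's immediate notice to the DSMB Chair.

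This rests on the wording of the protocol and on sections 1.3 and 1.4 counting as identification of bleeding by nature. It does not rest on any event rate, on the content of the brochure or monograph, or on what the regulation itself requires; the last two are outside the documents. The amendment should be made, but the documents do not show that any particular bleed would be withheld.

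**What to change.** Amend the protocol as follows.

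1. **Section 7.4.** Define expected as consistent in nature, severity *and* frequency with the reference document for that drug, and unexpected as any one of the three not consistent. State that frequency is judged on accumulated data and not on a single case.
2. **Reference source.** Delete the protocol as a source from both definitions. Name the investigator brochure or product monograph that applies to each of rivaroxaban, ASA and clopidogrel.
3. **SAE form, item 23.** Bring the *More prevalent* box into line with section 7.4 by treating it as unexpected for reporting.
4. **DSMB notice.** Reconcile section 7.5.3 with section 9.5.1 so that one rule says which SAEs are notified at once.

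The cost is a wording amendment with ethics board approval under section 9.2.1, a small change to one form, and possibly a few more expedited reports in a 40-participant trial. The documents give no basis for estimating how many.

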7.5 RECORDING, REPORTING AND FOLLOW-UP OF ADVERSE EVENTS

7.5.1 Adverse Events Recording

Adverse events will be recorded on the CRF.

The investigator and delegates will record all directly observed adverse events and all adverse events spontaneously reported by the participant. In addition, each participant will be questioned about adverse events at each visit.

7.5.2 Adverse Events Reporting

The QI or delegate will be responsible for reporting the AEs to the OHSNREB, and the Data and Safety Monitoring Board (DSMB) as follows:

- Adverse events will be reported to the OHSNREB as per their guidelines
- Adverse events will be summarized in a table, and provided to the Data and Safety Monitoring Board (DSMB) before DSMB meetings.

7.5.3 Serious Adverse Events Reporting

SAEs require prompt or immediate reporting to the QI or delegate. The QI is ultimately responsible for reporting the SAEs to Health Canada, the OHSNREB, the Data and Safety Monitoring Board and Bayer.

Reporting to Health Canada

Serious adverse events that are both unexpected and related or possibly related are subject to expedited reporting to Health Canada. SAEs that are expected or that are unrelated to the study drug are not reportable.

Report must be filed in the cases:

- I. where the SAE is neither fatal nor life-threatening; within 15 days after becoming aware of the information
- II. where it is fatal or life-threatening, immediately where possible and, in any event, within 7 days after becoming aware of the information

Within 8 days after having informed Health Canada of the SAE, the Qualified investigator will submit as complete as possible, a report which includes an assessment of the importance and implication of any findings.

Each SAE which is subject to expedited reporting should be reported individually using the RIFLE SAE form (see Appendix 2).

Any updated follow up information that becomes available regarding the SAE should be reported in a follow up report.

Reporting to the OHSNREB

All SAEs, will be reported to the OHSNREB as per their guidelines.

Reporting to the Data Safety Monitoring Board (DSMB)

SAEs, that are related or possibly related and unexpected will be reported immediately to the Chair of the DSMB .

All SAEs, whether related to the study interventions or not will be summarized in a table, and provided to the DSMB before each scheduled DSMB meeting

Reporting to Bayer

SAEs will be reported to Bayer as per procedure outlined in the grant agreement.

